3.5.2 Adverse events

3.5.2.1 Data handling

Adverse events will be coded using the Medical dictionary for regulatory activities (MedDRA) and assessed according to the Common Terminology Criteria for Adverse Events (CTCAE) version 4.03, respectively.

The CTCAE represents a comprehensive grading system for reporting the acute and late effects of cancer treatments. CTCAE grading is by definition a 5-point scale generally corresponding to mild, moderate, severe, life threatening, and death. This grading system inherently places a value on the importance of an event, although there is not necessarily proportionality among grades (a grade 2 is not necessarily twice as bad as a grade 1).

If CTCAE grading does not exist for an AE, grades 1, 2, 3, or 4 corresponding to the severity of mild, moderate, severe, and life-threatening, respectively, will be used. CTCAE grade 5 (death) is not used in this study. Death information will be collected on the "Death" eCRF pages.

Data analysis 3.5.2.2

AE Summaries (CSR outputs)

Primary AE summaries will include all AEs that started or worsened during the on-treatment period. Additional select summaries will be produced using all treatment related AEs starting or worsening during the on-treatment or post-treatment period.

All AEs collected in the AE (e)CRF page will be listed along with the information collected on those AEs e.g. AE relationship to study treatment, AE outcome etc. AEs starting during the preor post-treatment periods will be flagged in the listings.

AEs will be summarized by number and percentage of subjects having at least one AE, having at least one AE in each primary system organ class (SOC) and for each preferred term (PT) using MedDRA coding. A subject with multiple occurrences of an AE will be counted only once in the respective AE category. A subject with multiple CTCAE grades for the same preferred term will be summarized under the maximum CTCAE grade recorded for the event. AE with missing CTCAE grade will be included in the 'All grades' column of the summary tables.

In AE summaries the primary system organ class will be presented alphabetically and the preferred terms will be sorted within primary SOC in descending frequency. The sort order for the preferred term will be based on their frequency in all patients.

The following adverse event summaries will be produced by treatment for AEs starting or worsening during the on-treatment period:

- Overview of adverse events and deaths (number and % of subjects who died, with any AE, any SAE, any dose reductions/interruptions, AE leading to discontinuation)
- AEs by SOC and PT, summarized by relationship (all AEs and AEs related to study treatment);
- Seriousness (SAEs, and non-SAEs);
- Leading to treatment discontinuation;
- Leading to dose interruption/adjustment;
- Requiring additional therapy;
- Leading to fatal outcome;
- Dose limiting toxicities by PT

The following summaries will be produced for all AEs starting or worsening during the ontreatment or post-treatment periods:

- AEs related to study treatment by SOC and PT;
- SAEs related to study treatment

The following listings will be produced:

- All adverse events (safety set)
- Adverse events among subjects who were not treated (all screened subjects)

Deaths (CSR Outputs)

Separate summaries for on-treatment and all deaths (including post-treatment death) will be produced by system organ class and preferred term.

All deaths will be listed for the safety set, deaths occurring after the on-treatment period will be flagged. A separate listing of deaths prior to starting treatment will be provided for all screened subjects.

EudraCT and clinicaltrials.gov requirements for AEs and Deaths summaries

For the legal requirements of clinicaltrials.gov and EudraCT, two required tables on treatmentemergent adverse events which are not serious adverse events with an incidence greater than 5% and on treatment emergent SAEs and SAEs suspected to be related to study treatment will be provided by SOC and PT on the safety set population in the final CSR.

If for a same patient, several consecutive AEs (irrespective of study treatment causality, seriousness and severity) occurred with the same SOC and PT:

- a single occurrence will be counted if there is ≤ 1 day gap between the end date of the preceding AE and the start date of the consecutive AE
- more than one occurrence will be counted if there is > 1 day gap between the end date of the preceding AE and the start date of the consecutive AE

For occurrence, the presence of at least one SAE / SAE suspected to be related to study treatment / non SAE has to be checked in a block e.g., among AE's in a ≤ 1 day gap block, if at least one SAE is occurring, then one occurrence is calculated for that SAE.

The number of deaths resulting from SAEs suspected to be related to study treatment and SAEs irrespective of study treatment relationship, will be provided by PT.

Adverse events of special interest / grouping of AEs

An adverse event of special interest is a grouping of adverse events that are of scientific and medical concern specific to compound PDR001. These groupings are defined using MedDRA terms, SMQs (standardized MedDRA queries), HGLTs (high level group terms), HLT (high level terms) and PTs (preferred terms). Customized SMOs (Novartis MedDRA queries, NMO) may also be used. A NMQ is a customized group of search terms which defines a medical concept for which there is no official SMQ available or the available SMQ does not completely fit the need. It may include a combination of single terms and/or an existing SMQ, narrow or broad. For each specified AESI, number and percentage of subjects with at least one event of the AESI occurring during on-treatment period will be summarized.

Summaries of these AESIs will be provided by primary system organ class and/or preferred term and treatment.

A listing of all grouping levels down to the MedDRA preferred terms used to define each AESI will be generated.

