#### Section 10.5.3.1 and 10.5.3.2: Analysis set and grouping for the analyses

- Change of last day to On-treatment period definition from 150 days to 30 days after last dose of study medication (all patients will continue to be followed for 150 days after last dose)
- Change of Start date of post-treatment period from 151 days to 31 days after last dose of study medication
- Addition of safety summaries description

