### **Amendment 05 (30-Sep-2016)**

#### **Amendment rationale**

The protocol is amended to increase the duration of contraception and safety follow-up periods post PDR001 treatment from 90 days to 150 days, using five times the upper limit of the half-life of 23 days and an added safety margin. These changes are related to an Urgent Safety Measure communicated on 08-Jun-2016 to all investigators.

[REDACTED]

[REDACTED]

Therefore, after the start of a new antineoplastic therapy during the safety follow-up, only AEs and SAEs suspected to be related to PDR001 will be collected in order to focus on the collection of information relevant to PDR001; and concomitant medications will be recorded until the 30-day safety follow-up or the start of new antineoplastic, whatever occurred first.

Language relating to bone scans and other radiologic exams for evaluation of bone metastases is clarified.

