The emergence of acquired resistance to therapy is a major problem for patients with cancer, and understanding the mechanism of acquired resistance to immunotherapies is an urgent goal of current research. Under this amendment, language has been added to allow the collection of

tumor tissue upon the development of acquired resistance to treatment. The purpose of this sample is to identify changes in the tumor that may underlie treatment resistance.

Based on preliminary pharmacokinetic data and the possibility of delayed appearance of immune-related adverse events, the safety follow-up period has been extended to 90 days after the last dose of study treatment.

To align this protocol with the latest Novartis guidelines for the prevention of pregnancies in participants in clinical trials and their partners, the exclusion criteria were updated to exclude sexually active male subjects who are not willing to use a condom during the study.

Japan is no longer planning to participate in this global study, therefore the language specific for Japan was removed from the protocol.

Minor inconsistencies/clarifications were made throughout the document.

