### 7.1.6 Follow up period

All patients must have safety evaluations for 150 days after the last dose of study treatment. The evaluations can be done either by telephone call or visit for the 30-, 90-, and 150-day safety follow-up visits. Concomitant medications will be collected until the 30-day safety follow-up has been completed or the start of new antineoplastic therapy, whichever occurs first. If the 150-day safety evaluation is conducted by phone, samples do not need to be collected. Data collected should be added to the Adverse Events CRF, the antineoplastic therapies since discontinuation of study treatment CRF, the Concomitant Medications CRF, Biomarker blood sample CRF, and PK [REDACTED] CRFs. For PK [REDACTED] samples and Biomarker samples collection schedule is outlined in [Section 7.2.3](#) and [Section 7.2.4](#) respectively. For female patients of child bearing potential, pregnancy tests will be performed as outlined in [Section 7.2.2.5.7](#).

Patients who discontinue study treatment for any reason other than death, disease progression per irRC, clinical progression, lost to follow-up, consent withdrawal, start of new cancer therapy or study termination, also should return for tumor evaluation assessments and should not be considered withdrawn from the study until 80% of the patients in each disease group of the

phase II part have had progression of disease or discontinued the study for any reason. If patients refuse to return for these visits or are unable to do so, every effort should be made to contact them or a knowledgeable informant by telephone to determine if the patient had disease progression. Once the Follow up for Disease progression period ended, the End of Post treatment Phase disposition CRF should be completed.

Upon completion of the 150-day follow up or/and disease progression follow up, patients will be followed for survival every 3 months (can be done by telephone call) until death or until the end of the study is reached, unless they withdraw consent or are lost to follow-up.

Antineoplastic therapies since discontinuation of study drug will be collected during this follow-up period.

For patients who transfer to another clinical study or an alternative treatment option to continue provision of study treatment, as described in [Section 4.3](#), the follow-up for 150-day safety, disease progression and survival will not be performed.

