2.1.3.3 On-treatment assessment/event and observation periods

The overall observation period is divided into three mutually exclusive segments:

- 1. pre-treatment period: from day of patient's informed consent to the day before first dose of study treatment
- 2. on-treatment period: from day of first dose of study treatment to 30 days after last dose of study treatment
- 3. post-treatment period: starting at day 31 after last dose of study medication.

If dates are incomplete in a way that clear assignment to pre-, on-, post-treatment period cannot be made, then the respective data will be assigned to the on-treatment period.

Safety summaries (tables, figures) include only data from the on-treatment period with the exception of baseline data which will also be summarized where appropriate (e.g. change from baseline summaries). Following last administration of PDR001, adverse events (including serious adverse events), and new antineoplastic therapies are collected for a period of 150 days. Following start of new antineoplastic therapy, only study treatment related adverse events are collected. Select summaries of related adverse events will be produced for the combined ontreatment and post-treatment periods (Section 3.5.2.2).

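### AESI-group incidence stops at 30 days after last dose although adverse events are collected to day 150; one extra table from collected data would close the gap.

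*SAP*

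**What the plan says.** SAP Section 3.5.2.2 defines AESIs as groupings of events of particular concern for PDR001, built from standard and customised MedDRA queries and other MedDRA levels. For each grouping, the "number and percentage of subjects with at least one event of the AESI occurring during on-treatment period will be summarized". SAP Section 2.1.3.3 sets the window: "on-treatment period: from day of first dose of study treatment to 30 days after last dose of study treatment". The same section gives the general rule: "Safety summaries (tables, figures) include only data from the on-treatment period with the exception of baseline data".

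Collection runs longer. Protocol Section 7.1.6 states: "All patients must have safety evaluations for 150 days after the last dose of study treatment". Protocol Section 10.5.3.1 and SAP Section 3.5 confirm that adverse events are collected over those 150 days, restricted to treatment-related events once new antineoplastic therapy starts.

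SAP Section 3.5.2.2 also has a wider set of tables: "The following summaries will be produced for all AEs starting or worsening during the ontreatment or post-treatment periods". The list under that sentence has two items: treatment-related adverse events by system organ class and preferred term, and treatment-related serious events. AESIs are not on it. Protocol Section 10.5.3.2 says AESIs will be tabulated and sets no period specific to them, but its primary adverse event tables are on-treatment only.

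**The concern.** AESIs are the groupings in which the sponsor most wants to know how many patients had an event. The documents give two reasons to expect drug effects after day 30. The Amendment 05 rationale justifies 150 days of follow-up by "using five times the upper limit of the half-life of 23 days and an added safety margin". The Amendment 03 rationale, for the preceding extension, cites "the possibility of delayed appearance of immune-related adverse events, the safety follow-up period has been extended to 90 days". SAP Section 3.4 reasons similarly about benefit, counting responses up to the start of further antineoplastic therapy because response to immunotherapy may come late.

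A patient whose first AESI starts on day 31 or later enters no AESI rate. The combined-period related-event tables do not replace that rate, for two reasons. They spread one medical concept over several preferred-term rows, so patients cannot be counted once per concept. They also depend on the investigator's causality judgement, whereas the on-treatment AESI count is not limited to related events. At stake is a readable statement of how often these events occur over the whole period in which the trial looked for them.

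**Working it through.** **1. Which planned outputs reach past day 30 (SAP Section 3.5.2.2)?**

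| Output | Reaches past day 30? | Counts patients by AESI group? |
|---|---|---|
| AESI summary | No | Yes |
| Related adverse events by class and term | Yes | No |
| Related serious events | Yes | No |
| All deaths, including post-treatment | Yes | No |
| Listing of all adverse events, late ones flagged | Yes | No (no incidence) |
| Listing of terms that define each AESI | Not applicable | No (definitions only) |

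No output does both.

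**2. How much post-dose time is left out?** Inputs: 150 days of collection (Protocol Section 7.1.6) and 30 days of AESI window (SAP Section 2.1.3.3). 150 − 30 = 120 days; 120/150 = 80% of the post-dose segment. This fraction does not describe the whole AESI window, which also includes all time on treatment.

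**3. The plan's own figure of 150 days.** Input: 23-day upper-limit half-life (Amendment 05 rationale). 5 × 23 = 115 days, so 150 implies a margin of 150 − 115 = 35 days. The margin is not stated, so 150 is consistent with its inputs but cannot be derived exactly from them.

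**4. Drug remaining, as context only.** Assuming mono-exponential decline, the fraction remaining t days after the last dose is 0.5^(t/h). Half-lives: 23 days as above, and 10 to 20 days from Protocol Section 2.3.

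- h = 23, t = 30: 0.5^(30/23) = 0.5^1.30 = 40%.
- h = 23, t = 150: 0.5^(150/23) = 0.5^6.52 = 1.1%.
- h = 20, t = 30: 0.5^1.5 = 35%.
- h = 10, t = 30: 0.5^3 = 12.5%.

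**5. Position of day 30 relative to dosing.** On the every-4-weeks regimen the next dose would have been due on day 28, so the window ends 30 − 28 = 2 days later. On every 3 weeks it ends 30 − 21 = 9 days later.

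Steps 4 and 5 show that day 30 is not clear of drug. They say nothing about how many AESIs start after it.

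**The case against.** **The window is a documented choice.** Amendment 06 records: "Change of last day to On-treatment period definition from 150 days to 30 days after last dose of study medication". It kept the 150-day follow-up. Protocol Section 10.5.3.1 bases safety summaries primarily on the on-treatment period, and Section 10.5.3.2 extends only selected summaries of related events. The SAP follows both. This stands: there is no protocol–SAP contradiction and no oversight to correct.

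**Late events are reported.** Related ones are tabulated, deaths are summarised and every event is listed. With the listing of AESI-defining terms, a reader could pick out late cases by hand. This also stands, but hand-picking from listings is not an incidence, and late AESIs judged unrelated have no summary in AESI groups.

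**The proposed rate has mixed ascertainment.** After day 30, contacts may be by telephone and concomitant medications are no longer collected (Protocol Section 7.1.6). After new antineoplastic therapy only related events are collected. Patients transferred to another study or treatment option have no 150-day follow-up. The limits are real and belong in footnotes; they do not make the table uninformative.

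**Stronger readings the documents do not support.** A reader might infer that the planned AESI rates are biased downward. They are not: a rate labelled on-treatment is valid for its window. A reader might take the 40% residual drug as the share of events missed, but residual drug is not an event rate. A reader might attribute the 150 days to late immune events, but the delayed-immune-event reason was given for the 90-day extension and the half-life reason for 150 days. Nor do the documents list the AESIs, so treating them as mainly immune events is an inference.

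**Conclusion.** The point holds as a reporting gap. No planned summary gives AESI-group incidence that includes events starting on days 31 to 150 after the last dose. The on-treatment rate can understate incidence over the full collection period whenever a patient's first event in a group starts after day 30. The documents give no late event rates, so the size of that understatement cannot be estimated. The residual-drug figures rest on mono-exponential decline and serve only as context. The primary endpoints, sample size and decision rules are unaffected. I would label this a cheap improvement.

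**What to change.** Keep the on-treatment AESI table. In SAP Section 3.5.2.2 add the same summary, with the same groupings, for the combined on- and post-treatment period to day 150: all events regardless of causality until the start of new antineoplastic therapy, and treatment-related events only from then on. Show the two windows side by side.

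Footnote three limits: collection is related-only after new antineoplastic therapy, late contacts may be by telephone, and transferred patients have no 150-day follow-up.

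The cost is one table from data and groupings that already exist, introduced by SAP amendment before database lock or by addendum after it, as SAP Section 1 provides. The downside is slightly higher percentages that include some background events and mix two levels of ascertainment; presenting both windows together keeps that visible.

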3.5.3 Laboratory data

3.5.3.1 CTC grading for laboratory parameters

Grade categorization of lab values will be assigned programmatically as per NCI Common Terminology Criteria for Adverse Events (CTCAE) version 4.03. The calculation of laboratory CTC grades will be based on the observed laboratory values only, clinical assessments will not be taken into account. The criteria to assign CTC grades are given in Novartis internal criteria for CTC grading of laboratory parameters. The latest available version of the document based on the underlying CTCAE version 4.03 at the time of analysis will be used.

For laboratory tests where grades are not defined by CTCAE v4.03, results will be graded by the low/normal/high (or other project-specific ranges, if more suitable) classifications based on laboratory normal ranges.

A severity grade of 0 will be assigned for all non-missing lab values not graded as 1 or higher. Grade 5 is not applicable. For laboratory tests that are graded for both low and high values, summaries will be done separately and labeled by direction, e.g., sodium will be summarized as hyponatremia and hypernatremia.

3.5.3.2 Imputation rules

CTC grading for blood differentials is based on absolute values.

If laboratory values are provided as '<X' (i.e. below limit of detection) or '>X', prior to conversion of laboratory values to SI unit, these numeric values are set to X.

The following rules will be applied to derive the WBC differential counts when only percentages are available for a xxx differential

xxx count = (WBC count) * (xxx %value / 100)

Corrected calcium can be derived using the reported total calcium value and albumin at the same assessment using the following formula:

Corrected Calcium (mg/dL) = Calcium (mg/dL) - 0.8 [Albumin (g/dL)-4]

In order to apply the above formula, albumin values in g/L will be converted to g/dL by multiplying by 0.1), calcium values in mmol/L will be converted to mg/dL by dividing by 0.2495. For calculation of laboratory CTC grades 0 and 1, the normal range for derived corrected calcium is set to the same limits (in mg/dL) as for calcium.

CTC grades for the derived absolute WBC differential counts (neutrophils, lymphocytes) and corrected calcium are as defined in the previous section.

3.5.3.3 Data analysis

On analyzing laboratory, data from all sources (central and local laboratories (as applicable)) will be combined. The summaries will include all assessments available for the lab parameter collected no later than 30 days after the last study treatment administration date (see Section 2.1.3.3).

The following listing will be produced for the laboratory data:

• Listing of all laboratory data with values flagged to show the corresponding CTCAE 4.03 grades if applicable and the classifications relative to the laboratory normal ranges

The following summaries will be generated separately for hematology and biochemistry tests:

For laboratory tests where grades are defined by CTCAE 4.03:

- Worst post-baseline CTCAE grade (regardless of the baseline status). Each patient will be counted only once for the worst grade observed post-baseline.
- Shift tables using CTCAE 4.03 grades to compare baseline to the worst on-treatment value

For laboratory tests where grades are not defined by CTCAE 4.03:

• Shift tables using the low/normal/high/ (low and high)

Table 3-3 lists all laboratory parameters for which CTCAE grades are defined.

Table 3-3 Laboratory parameters to be listed and presented in grade shift tables based on CTC grade

Hematology and coagulation		Biochemistry	
White Blood Cells (WBC)	$\uparrow\downarrow$	Albumin	\downarrow
Hemoglobin	\downarrow	Alkaline phosphatase	↑
Platelets counts	\downarrow	ALT (SGPT)	↑
Absolute Neutrophils	\downarrow	AST (SGOT)	↑
Absolute Lymphocytes	$\uparrow\downarrow$	Glucose	$\uparrow\downarrow$

Novartis	Confidential			Page 40
SAP final CSR	24-Jul-2020 (11:48)			CPDR001X2101
	activated partial thromboplastin time (APTT)	1	Calcium	$\uparrow\downarrow$
	International normalized ratio (INR)	↑	Total Bilirubin	↑
			Creatinine	↑
			Potassium	$\uparrow\downarrow$
			Magnesium	$\uparrow\downarrow$
			Sodium	$\uparrow\downarrow$

[↑] Indicates that CTC grade increases as the parameter increases, these parameters are to be included in the summary of maximum post-baseline lab parameters

Table 3-4 lists all laboratory parameters to be listed based on local laboratory normal ranges.

Table 3-4 Laboratory parameters to be listed based on local laboratory normal ranges

_	
Hematology and coagulation	Biochemistry
Absolute eosinophils	Urea
Absolute basophils	Blood urea nitrogen (BUN)
Absolute monocytes	Direct bilirubin
	Indirect bilirubin
	Bicarbonate
	Chloride
	T4
	TSH
	IL-6
	IFN-γ

